9.4.2 ANALYSIS OF THE PRIMARY EFFICACY ENDPOINT(S)

The primary endpoint is the difference between treatment groups in the change of 6-minute walk distance (6MWD) between baseline and 24 weeks. Linear regression will be performed with the change in 6MWD between baseline and 24 weeks as outcome and treatment group as the primary predictor of interest, adjusted for baseline 6MWD and baseline NYHA functional class as the stratification variable. The estimate of the treatment effect will be provided with associated 95% confidence interval (CI).

Missing 6MWD at 24 weeks will be imputed as follows. Subjects known to be dead before the 24 week assessment will have zero imputed for their 24 week 6MWD. Missing 24 week 6MWD for subjects who are alive will be imputed using multiple imputation. The imputation model will have prognostic variables as the predictor variables. Prognostic variables will include age, gender, and etiology of pulmonary hypertension, baseline six minute walk test, baseline right ventricular diameter, and baseline BNP. The multiple imputation will use Markov Chain Monte Carlo (MCMC), which assumes that the variables in the imputation model have a joint multivariate normal distribution (MVN). The number of imputations to be performed will be 100. One hundred is selected because it is not too large that it requires heavy computations and is not too small (such that the Monte Carlo error is still small enough at around 0.1 times the standard deviation). The “proc mi” procedure in SAS will be used to impute the missing observations.

Although every effort will be made to avoid missing data, a range of approaches to missing 6MWD will be considered as sensitivity analyses representing a range of conservative and anti-conservative biases to describe the range of possible differences.

Sensitivity Analyses of the Primary Endpoint

Sensitivity analyses of the primary endpoint will include:

- a linear regression model using a worst case scenario (WCS) method of imputation
 - a linear regression model of the 24 week 6MWD without imputation (complete case analysis)
- (1) The worst case scenario method of imputation will impute zero for all missing 6MWD at week 24.
(2) The linear regression method will model the 24 week 6MWD on treatment assignment, adjusting for baseline 6MWD and baseline NYHA class using least squares and robust standard error estimates. For all methods, treatment effect estimates and 95% CIs will be presented.

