4 ANALYSIS SETS

4.1 Analysis Set Definitions

The following Analysis sets will be evaluated and used for presentation and analysis of the data:

- **Screening Analysis Set:** Includes all subjects who signed the informed consent form.
- **Enrolled Analysis Set:** Includes all subjects in the Screening Analysis Set who were assigned a randomized treatment.
- **Full Analysis Set (FAS):** Includes all randomized subjects who received at least 1 dose of study medication. Subjects will be analyzed according to their randomized treatment.
- **Per Protocol (PP) Set 1 (PPS1):** Includes all subjects in the FAS whose famotidine medication reconciliation suggest adherence to study drug for 80% or more of administered doses. Subjects will be analyzed according to their randomized treatment.
- **Per Protocol (PP) Set 2 (PPS2):** Includes all subjects in the FAS who (1) were randomized to famotidine for whom H₂ receptor antagonists are detected by mass spectrometry at the final visit and (2) those randomized to placebo for whom H₂ receptor antagonists are not detected at the final visit. Subjects will be analyzed according to their randomized treatment.
- **Safety Analysis Set (SAF):** Includes all randomized subjects who received at least 1 dose of study medication. Subjects will be analyzed according to their actual treatment. Actual treatment is defined as the treatment received for most of the days during the treatment phase of the study.

Per ICH-E9 [1] and ICH-E9-R1 [2] guidelines, will use FAS instead of intention-to-treat. The FAS will be the primary analysis set for the analysis of the primary and secondary efficacy endpoints.

The PPS1 and PPS2 will be used in the sensitivity analyses of the primary and secondary efficacy endpoints.

The SAF will be the primary set for the analysis of the safety parameters.

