5.4 Withdrawals, Dropouts, Loss to Follow-up

Discontinued subjects will not be replaced whether they received or did not receive the study drug. The multiple imputation approach is included in Section 6.4.

Follow-up of subjects who discontinued the study drug early will continue until Week 24 and the study procedures will be assessed as per the schedule of assessment (see Table 9-1).

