6.2.3 Adjustments for Covariates

Subject randomization will be stratified by NYHA/WHO Functional Class (NYHA/WHO Functional Class II versus Class III/IV) to ensure balanced representation of this important marker of severity.

For continuous outcome variables, baseline values of the dependent variable and NYHA functional class (as a binary stratification variable) will be included in the statistical model .

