6.2.6 Missing, Unused, and Spurious Data

The handling of intercurrent events (ICEs) and sensitivity analyses are described in Section 6.4. No other imputation of missing efficacy endpoints will be used.

In all listings, missing or incomplete dates in safety data will be left as they have been recorded. However, for calculation and sorting based on dates and for consideration in summary tables, the following method will be used:

For partial or missing adverse event (AE) start dates the following imputation will be applied:

1. If year is not missing and is after the year of first dose:
 - a. If month is missing, then month will be imputed as January.
 - b. If day is missing, then day will be imputed as the first of the month.

2. If year is not missing and is the same as the year of the first dose:
 - a. If month is missing, then impute the month as the month of the first dose date.
 - b. If day is missing, and the month is the same as the month of the first dose date, then impute day as the day of the first dose date.
 - c. If day is missing but month is after the month of first dose date, then impute day as the first day of the month.
3. If year is missing then impute the year as the year of the first dose date:
 - a. If month is missing, then impute the month as the month of the first dose date.
 - b. If day is missing, then impute the day as the day of the first dose date.
4. If the start date is completely missing, but the AE is either ongoing or the stop date is after the first dose date then impute the start date as the first dose date.
5. For any cases involving the rules above, if the AE end date is before the AE start date, then do not impute the AE start date and assume that the AE is treatment emergent for the purpose of the analysis. Further, if the AE stop date occurs prior to the first dose date, do not impute the AE start date, and assume that the AE is not treatment emergent.

No imputations will be applied to AE stop dates.

A missing/incomplete date of medical comorbidities or disease diagnosis will be assumed to have occurred before any study treatment.

Missing AE relationship data will be assigned the 'related' category for treatment emergent AE.

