6.4.1 Primary efficacy analysis

The primary endpoint is the difference between treatment groups in the change of 6-minute walk distance (6MWD) between baseline and 24 weeks. Linear regression will be performed for the FAS with the change in 6MWD between baseline and 24 weeks as outcome and treatment group as the primary predictor of interest, adjusted for baseline 6MWD and baseline NYHA functional class as the stratification variable. The estimate of the treatment effect will be provided with associated 95% confidence interval (CI).

Missing 6MWD at 24 weeks will be imputed as follows. Subjects known to be dead before the 24 week assessment will have zero imputed for their 24 week 6MWD. Missing 24 week 6MWD for subjects who are alive will be imputed using multiple imputation. The imputation model will have prognostic variables as the predictor variables. Prognostic variables will include age, gender, and etiology of pulmonary hypertension, baseline six minute walk test distance, baseline right ventricular diameter, and baseline BNP. The multiple imputation will use Markov Chain Monte Carlo (MCMC), which assumes that the variables in the imputation model have a joint multivariate normal distribution (MVN). The number of imputations to be performed will be 100. One hundred is selected because it is not too large that it requires heavy computations

and is not too small (such that the Monte Carlo error is still small enough at around 0.1 times the standard deviation). The “proc mi” procedure in SAS will be used to impute the missing observations.

PAH etiology in the analysis will be as follows:

- Idiopathic
- Familial
- Congenital Heart Disease
- Collagen Vascular Disease
- Toxin
- Portopulmonary Hypertension

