9.2 Estimands

Not applicable.

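### The primary multiple-imputation model omits treatment arm, so under missing at random the 6MWD effect shrinks toward zero by about the share of participants imputed

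*SAP*

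**What the plan says.** The primary analysis is a linear regression of change in 6MWD with "treatment group as the primary predictor of interest, adjusted for baseline 6MWD and baseline NYHA functional class as the stratification variable" (SAP 6.4.1). Deaths before Week 24 are scored zero. Living participants with no Week 24 value are multiply imputed, 100 times, under a multivariate normal model.

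The rule for that model, in Protocol 9.4.2 and repeated in the SAP, is: "The imputation model will have prognostic variables as the predictor variables". The SAP then lists them: "Prognostic variables will include age, gender, and etiology of pulmonary hypertension, baseline six minute walk test distance, baseline right ventricular diameter, and baseline BNP". The protocol's list is the same in substance. Neither list names randomized arm or NYHA stratum, and neither document says to impute separately by arm.

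Three other SAP sections bear on the point:
- **6.2.3** says that for continuous outcomes "NYHA functional class (as a binary stratification variable) will be included in the statistical model". It does not mention the imputation model.
- **6.2.6** says "No other imputation of missing efficacy endpoints will be used". This limits which imputations are done; it adds no predictor.
- **9.2**, on estimands, is marked as not applicable, so no assumption about drug effect in missing participants is stated there.

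Sections 6.4.2.1 to 6.4.2.6 impute each secondary endpoint by analogy with the primary.

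**The concern.** An imputation model should contain every term of the analysis model, above all the term whose coefficient is the result. If arm is left out, imputed values in both arms come from one regression fitted to the two arms combined. The imputed participants then carry no expected treatment difference and dilute the difference seen in those observed.

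Multiple imputation from baseline predictors rests on missing at random: given the covariates, a missing participant would have shown the same effect as an observed one. Under that assumption the dilution is bias. The interval is affected too, because Rubin's standard error becomes larger than the true sampling SD. What is at stake is the headline estimate, its confidence interval and some power. A false positive is not the risk.

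**Working it through.** **Inputs.** From SAP 2.2: 80 participants, 1:1, so 40 per arm. From SAP 6.1: effect 31.9 m, SD 37.6 m, about 10% attrition. From SAP 6.2.1: two-sided alpha 0.05. The SAP does not say which SD 37.6 m is; it is taken here as the residual SD.

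**The plan's own figure.** A two-sample noncentral t calculation gives power 0.963 at 40 per arm and 0.944 at 36 per arm. These reproduce the 0.96 and 0.94 in Table 6-1. Both assume the full 31.9 m effect.

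**Expected estimate as written.** Let m be the multiply imputed share in each arm, δ the true effect and p the famotidine share among those observed. Leaving covariates aside, each imputed value has expectation μ₀ + pδ in either arm.
- Famotidine mean: (1 − m)(μ₀ + δ) + m(μ₀ + pδ)
- Placebo mean: (1 − m)μ₀ + m(μ₀ + pδ)
- Difference: (1 − m)δ

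At m = 5% this is 0.95 × 31.9 = 30.3 m. At m = 10% it is 0.90 × 31.9 = 28.7 m. With unequal shares m₁ (famotidine) and m₀ (placebo) the factor is (1 − m₁) + p(m₁ − m₀). For 15% and 5%, p = 0.85/1.80 = 0.472, giving 0.85 + 0.472 × 0.10 = 0.897, so the average share remains a good guide.

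**Simulation under missing at random.** 6,000 trials per row, using the SAP's predictors (six-level etiology as five indicators), 100 Bayesian-regression imputations and Rubin pooling. This is equivalent to the multivariate normal model when only Week 24 is missing. Assumptions not in the documents: etiology mix 40/3/12/25/15/5%, a baseline slope of −8 m per SD, and −5 m for NYHA III/IV. No deaths.

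| Imputed | Imputation model | Estimate (m) | Mean SE | Empirical SD | Power | Rejection, no true effect |
|---|---|---|---|---|---|---|
| 5% | As written | 30.51 | 8.94 | 8.37 | 0.933 | 0.038 |
| 5% | + arm + NYHA | 32.14 | 8.83 | 8.81 | 0.948 | 0.048 |
| 10% | As written | 28.57 | 9.37 | 8.10 | 0.882 | 0.025 |
| 10% | + NYHA only | 28.53 | 9.38 | 8.10 | 0.883 | – |
| 10% | + arm + NYHA | 31.77 | 9.19 | 8.99 | 0.925 | 0.043 |
| 10% | None (complete case) | 31.77 | 8.94 | 8.92 | 0.934 | 0.048 |

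Adding NYHA alone changes nothing, so the missing arm term is the cause. A second simulation with different covariate effects and etiology mix gave 0.948 of the true effect at 5% imputed and 0.892 at 10%, with power about 0.88 as written at 10%.

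**If missing at random is wrong** (10% imputed, 4,000 trials each):

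| Effect in missing participants | True average (m) | As written (m) | + arm + NYHA (m) |
|---|---|---|---|
| Half | 30.30 | 28.71 | 31.92 |
| None | 28.71 | 28.62 | 31.85 |

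**How large the imputed share could be.** 10% is an upper end. Deaths are handled separately. The full analysis set "Includes all randomized subjects who received at least 1 dose of study medication", so never-dosed participants are outside it. SAP 5.4 adds "Follow-up of subjects who discontinued the study drug early will continue until Week 24". Under SAP 5.5, withdrawal or unscheduled visits from Day 126 to Day 175 count as Week 24.

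**The case against.** The strongest reply is that the added arm term makes an assumption of its own. People who only stop the drug stay in follow-up, so those still missing are mainly withdrawn or lost, and the withdrawal reasons in Protocol 7.1 include deterioration, drug-related serious events and inability to stay on study drug. For them, no effect may be more natural than full effect. The second table supports this: with no effect in the missing, the plan is off by 0.09 m and the added-arm model by 3.14 m; with half the effect, the two miss by about the same amount (1.59 m low, 1.62 m high). Even under missing at random, root-mean-square error at 10% is √(3.33² + 8.10²) = 8.8 m as written against √(0.13² + 8.99²) = 9.0 m.

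This stands as a limit on the bias claim, but not as a defence of the text. No section states a no-effect assumption or presents pooled imputation as deliberately conservative. SAP 6.4.1.1 puts conservative and anti-conservative approaches among the sensitivity analyses. Missing is also not the same as off drug: a participant on drug but tested after Day 175 has no analysis visit and, read literally, would be imputed. Similar mean squared error does not repair the bias or the miscalibrated interval.

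Other replies:
- *The list may not be exhaustive.* A programmer might add arm. But the governing rule admits prognostic variables only, and the two readings give different primary results.
- *The complete-case analysis contains arm and would show the gap.* True, but it is a sensitivity analysis.
- *The loss is small at 5%.* True: 0.948 − 0.933 = 0.015 in power.
- *The powers assume no deaths.* True, and zero-scored deaths matter. With one death per arm, 5% imputed and an assumed baseline mean of 400 m, a separate simulation gave power of about 0.30 as written and 0.37 with the fix. The absolute powers change; the direction does not.
- *Secondary endpoints are asserted without size.* True. No magnitude is claimed, and the categorical endpoints follow a cited method that is not in the documents.

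**Conclusion.** The concern holds and should be fixed. The imputation model as written omits treatment arm, and under missing at random it attenuates a true benefit by about the imputed share. That is about 1.6 m of 31.9 m at 5% and 3.2 m at 10%. At 10%, Rubin's standard error averages 9.4 m against a true SD of 8.1 m, and power falls by 0.925 − 0.882 = 0.043. The resulting 0.88 is below the 0.94 that SAP 6.1 states with 10% attrition.

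The attenuation factor follows from algebra and barely depends on the assumed covariate effects. The power figures rest on 40 per arm, a residual SD of 37.6 m, equal missing numbers in each arm and no deaths. The bias claim depends on missing at random; if missing participants have no drug effect, the plan as written is about right for the average effect. Type I error is not inflated under either assumption.

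**What to change.** In SAP 6.4.1, add randomized arm and the binary NYHA stratum to the PROC MI model so that it contains every analysis-model term, and state that the primary analysis assumes missing at random. Apply the same to the imputation of each secondary endpoint in 6.4.2. If an analysis assuming no drug effect in missing participants is wanted, name it as a sensitivity analysis in 6.4.1.1.

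Do not impute separately by arm. The listed predictors make 10 covariate columns (age, sex, five etiology indicators and three baseline measures) for about 36 observed participants per arm. Week 12 6MWD could be added as an auxiliary variable, but its gain depends on a correlation the documents do not give.

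Record the change in SAP Section 7, because Protocol 9.4.2 carries the same list. The cost is one or two sentences in 6.4.1, one entry in Section 7 and two variables that are already collected.

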6.4.1.1 Sensitivity analysis

Sensitivity analyses will be performed using the PPS1 and PPS2 analysis sets instead of FAS.

Although every effort will be made to avoid missing data, a range of approaches to missing 6MWD will be considered as sensitivity analyses representing a range of conservative and anti-conservative biases to describe the range of possible differences.

Sensitivity analyses of the primary endpoint will include:

- 1) • a linear regression model using a worst case scenario (WCS) method of imputation
- 2) • a linear regression model of the 24 week 6MWD without imputation (complete case analysis)

(1) The worst case scenario method of imputation will impute zero for all missing 6MWD at week 24.

(2) The linear regression method will model the 24 week 6MWD on treatment assignment, adjusting for baseline 6MWD and baseline NYHA functional class using least squares and robust standard error estimates.

For all methods, treatment effect estimates and 95% CIs will be presented.

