and pregnancy test if indicated. The pregnancy test can be performed as either a blood or urine test. A blood-based pregnancy test is preferred; however, if a urine test is used then it must be performed by study personnel and documented in the medical record. All participants will have serum collected for mass-spectrometry at the end of the study to evaluate for contamination of the study question by individuals taking over-the-counter H2 receptor antagonists. Serum, plasma, and blood for RNA isolation will be collected and stored for participants.

Adverse events and concomitant medications will be assessed and collected at all visits.

Optional Right Heart Catheterization (RHC) Evaluation: Subjects will have the option to take part in the RHC portion of the study that will be performed within 14 days of the Baseline Visit and within 7 days of the Week 24 Visit. The baseline visit must be done while not taking study drug and the week 24 visit must be done while taking study drug. This is a procedure which is performed for all patients with PAH. The purpose of this optional evaluation is to track changes in the measurements of the subjects' heart and lungs that might be related to study treatment with famotidine. 1% lidocaine local anesthesia will be used. It will take 3-4 hours to complete the right heart catheterization. On the day of the right heart catheterization, subjects will check into the cardiac catheterization laboratory at the University of Washington Medical Center. A nurse will check the subject's vital signs and basic bloodwork to make sure that the procedure is safe to perform. Once this is done, subjects will go into the cardiac catheterization laboratory where [name] will numb the area for the procedure with lidocaine. This will typically be the right side of the neck. After numbing the area, [name] will place a catheter into a vein, the right atria, right ventricle, and pulmonary artery and measure pressures at each position and check to see how much blood the heart is pumping. The process of inserting the catheter and taking measurements normally takes approximately 20-30 minutes. After these measurements, the catheter will be removed, a nurse will hold pressure on the area to ensure that there is no bleeding, and the subject will then be free to go.

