9.3 POPULATIONS FOR ANALYSES

Intent-to-Treat Population: All subjects who are randomized will comprise the intent-to-treat (ITT) population. The ITT population will be analyzed for the primary and secondary endpoint analyses and will comprise the safety population used for all safety analyses.

Per Protocol Population: Subjects in the ITT population whose famotidine medication reconciliation suggest adherence to study drug for 80% or more of administered doses will be evaluated as the per protocol population. The per-protocol population will be used in the sensitivity analyses of the primary and secondary endpoints. A second per protocol population will include participants for whom H₂ receptor antagonists are detected by Mass Spectrometry at the final visit relative to those for whom H₂ receptor antagonists are not detected.

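### PPS2 membership needs a final-visit assay result, so famotidine participants who die before Week 24 always leave that sensitivity analysis, and the plan does not say what happens to placebo participants without a sample

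*SAP*

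**What the plan says.** SAP 6.4.1 runs the primary regression in the FAS and makes death part of the endpoint: "Subjects known to be dead before the 24 week assessment will have zero imputed for their 24 week 6MWD". SAP 6.4.1.1 then adds: "Sensitivity analyses will be performed using the PPS1 and PPS2 analysis sets instead of FAS". It changes the analysis set and gives no other rule for deaths. SAP 6.4.2 reuses PPS2 for the secondary endpoints.

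SAP 4.1 admits two groups from the FAS to PPS2: participants who "were randomized to famotidine for whom H₂ receptor antagonists are detected by mass spectrometry at the final visit", and "those randomized to placebo for whom H₂ receptor antagonists are not detected at the final visit". Neither limb says what happens when there is no sample.

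The schedules in both documents show the assay at Baseline and Week 24 only. Protocol 8.1 agrees on timing: "All participants will have serum collected for mass-spectrometry at the end of the study". The second per-protocol population in Protocol 9.3 also rests on detection at the final visit.

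**The concern.** A per-protocol set should ask whether the primary result holds among people who took what they were assigned. PPS2 also selects on being alive and sampled at Week 24, and survival is part of the primary outcome. A famotidine participant who dies on treatment cannot have a qualifying positive result. A baseline sample does not help: it is taken before the first dose, and regular H2-antagonist users are excluded.

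If PPS2 and the FAS then disagree, the reader cannot tell whether the cause is adherence and contamination or the removal of deaths.

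The plan foresees deaths. Class IV patients are eligible, Protocol 8.2.3.3 lists cardiac arrest and sudden cardiac death among expected events over 24 weeks, and the SAP has a death rule. The two per-protocol sets can also treat the same death differently: PPS1 uses pill counts over actual exposure (SAP 6.3.4), so a participant who died can qualify for it.

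**Working it through.** **Inputs from the SAP.** 80 participants randomised 1:1, so 40 per arm (2.2); target difference 31.9 m and SD 37.6 m (6.1); two-sided 0.05 (6.2.1); linear regression of change on treatment, baseline 6MWD and NYHA stratum (6.4.1).

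**Assumptions not in the documents.** 0 to 4 deaths per arm; mean baseline 6MWD of 300 to 450 m, with 400 m as the worked value; baseline SD 100 m in the simulations. SAP 6.1 calls 37.6 m the SD of 6MWD. It is used here as the SD of change among survivors.

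**The plan's own figure.** A two-sample noncentral-t calculation with 31.9 and 37.6 gives power 0.963 at 40 per group and 0.944 at 36, against 0.96 and 0.94 in Table 6-1. It matches the other four entries too. This confirms the arm size and SD used here; it does not bear on PPS2 itself.

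**Formulas, no drug effect in survivors.** Let B be mean baseline, kF famotidine deaths and kP placebo deaths. A death scored 0 m has a change of about −B.

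- FAS: (kP − kF) × B/40.
- PPS2, no sample means excluded in both arms: about 0 for any kF and kP.
- PPS2, no sample counted as negative: famotidine deaths leave and placebo deaths stay, giving kP × B/40.

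Per placebo death kept: 300/40 = 7.5 m; 400/40 = 10 m; 450/40 = 11.25 m.

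**Simulation of the SAP model** (4,000 runs per row, B = 400 m, no drug effect; last column nominally 2.5%):

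| Deaths, famotidine / placebo | FAS | PPS2, deaths dropped | PPS2, placebo deaths kept | Kept: p<0.05 favouring famotidine |
|---|---|---|---|---|
| 0 / 0 | 0 m | 0 m | 0 m | 3% |
| 1 / 1 | 0 m | 0 m | +10 m | 3% |
| 2 / 2 | 0 m | 0 m | +20 m | 6% |
| 3 / 3 | 0 m | 0 m | +30 m | 15% |
| 4 / 4 | 0 m | 0 m | +40 m | 31% |
| 4 / 0 | −40 m | 0 m | 0 m | 2% |
| 4 / 2 | −20 m | 0 m | +20 m | 5% |
| 0 / 4 | +40 m | 0 m | +40 m | 36% |

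The simulated means agree with the formulas. Significance moves less than the estimate because each 0 m value also inflates the residual variance. Dropping deaths works in both directions: in the last row it removes a survival advantage.

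**Deaths dropped, with a true +31.9 m in survivors.**

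- 3 famotidine and 0 placebo deaths: FAS = (37 × 31.9 − 3 × 400)/40 = −0.5 m, with favourable p<0.05 in about 0.1% of runs. PPS2 is about +32 m, with favourable p<0.05 in 94% to 96% across repeated simulations.
- 1 famotidine and 0 placebo deaths: FAS = (39 × 31.9 − 400)/40 = +21.1 m (favourable p<0.05 in about 26%). PPS2 is about +32 m (96%).

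The first case was chosen so that the FAS nets to about zero. It shows how far the two sets can part, not what is likely.

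**The case against.** The strongest reply is that PPS2 is only a sensitivity set in a plan that counts deaths elsewhere. The FAS analysis scores known deaths as 0 m, and the worst-case analysis scores every missing value as 0 m. SAP 6.3.1 already requires the size of each analysis set and a listing of reasons for exclusion from the per-protocol sets; SAP 6.6.1 requires a listing of deaths. A reader might infer that the plan conceals mortality. The documents do not support that. What is missing is a count by arm beside the PPS2 estimate.

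Second, both limbs of the definition refer to an assay finding at the final visit, so excluding anyone without a result, in both arms, is the ordinary reading. The asymmetric shift depends on the less natural one. This stands, and is why the survivors-only form is the main point.

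Third, dropping deaths is not unique to PPS2. The complete-case analysis uses no imputation, and the 0 m for deaths is itself imputed, so on a plain reading it drops deaths as well. That is true, but it is labelled as a missing-data analysis, whereas PPS2 is offered as an adherence check.

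Fourth, keeping deaths puts unverified exposure into a set meant to verify it. This is a real cost. It is small if deaths are few, and it can be disclosed.

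**Conclusion.** The point holds as a defect in one sensitivity set. Under either reading, PPS2 membership depends on surviving to Week 24 in the famotidine arm, although death before Week 24 is scored in the endpoint. With exclusion in both arms, PPS2 is a survivors-only comparison: at an assumed 400 m baseline it shows about 0 m where the FAS would show −40 m for 4 versus 0 deaths. If a missing sample counts as negative, the shift toward famotidine is 7.5 to 11 m per placebo death. About three or four deaths per arm would then match the 31.9 m target, depending on baseline.

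Three stronger inferences fail.

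- The primary result is not compromised: the FAS and worst-case analyses are untouched.
- PPS2 does not readily produce a significant false benefit. Even on the less natural reading, favourable significance is about 3% with one death per arm and 6% with two, against 2.5%.
- PPS2 is not uninformative: it still describes attendees with samples.

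With no deaths before Week 24, this route has no effect. Death counts and baseline mean are assumptions; the documents give neither. An unscheduled sample taken at an early-withdrawal visit before a death would be an exception, but the schedule does not provide for one. The SAP should be amended; the fault does not threaten the trial's main conclusion.

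**What to change.** For 6MWD, in SAP 4.1 and 6.4.1.1:

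- Keep participants known to have died before Week 24 in PPS2 in both arms, scored 0 m as in the FAS.
- Exclude living participants with no final assay result from PPS2, in both arms.
- Show deaths and missing assays by arm beside the PPS2 estimate.
- Record the change in SAP section 7, because it departs from the detection-based population in Protocol 9.3.

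With this rule, equal deaths in the two arms give about 0 m when the drug has no effect, and 4 versus 0 famotidine deaths give about −40 m at a 400 m baseline, as in the FAS.

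For the secondary endpoints in SAP 6.4.2, require an available assay result in both arms and report deaths by arm. The 6MWD rule cannot simply be carried over, because the plan states no value for death in the main analysis of those endpoints.

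The cost is SAP wording and a small addition to one output; no new visits or data are needed. The downside is that exposure in the few participants who died is not confirmed by assay, which a footnote should state.
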